7.1 Timing of Analyses

In the non-blinded total of 300 subjects enrolled, the interim analysis will be performed at the enrollment of 150 subjects (at least 30 non-anesthesia patients enrolled) during the study period. at

the nominal significance level using OBrien-Fleming to determine α =0.00153. The final analysis will be performed at the end of 300 subjects enrolled. The nominal significance level is using OBrien-Fleming to determine α =0.02450.

7.2 Analysis Populations

(ICH E3; 9.7.1, 11.4.2.5. ICH E9; 5.2)

In our study design, both experimental and reference devices are set on all patients enrolled. The analysis is comparing the recording of devices on identical subjects. Therefore, all of the intending to treat patients are included in our study. However, if the patients were at risk of life-threatening events during their operation, the medical crew is obligated to proceed with resuscitation and stop the intervention, in such case, the recording could be terminated and the previous data is still counted in our study.

| Population | Definition / Criteria | Analyses Evaluated |
|-----------------|--|---|
| Safety | All subjects who are enrolled in the study. This population will be based on the operation the subject actually received. | Safety Adverse events/Adverse devices related events. |
| Intent To Treat | Comprise of all subjects with at least 5 minutes recording to evaluate the efficacy. This population will be based on the recording of both devices to the subjects enrolled. | Efficacy |
| Per-Protocol | The per-protocol population is a subset of the ITT population in this study. Subjects who were enrolled in the study and recorded by both devices for more than 5 minutes will be part of the ITT groups and the subjects with a protocol violation that is deemed to affect efficacy assessments in the study period, but their data will be | Per Protocol Population. |

Evaluating the Non-Inferiority of Airmod to Capnostream[™]35 on Respiratory Rate Monitoring and User Experience Clinical Evaluation

| excluded from the period(s) affected by the protocol violation for a PP analysis. (For instance, a patient who was administrated with an advanced airway management tool (LMA) should be considered as a protocol violation in the intraoperative period.) | | |
|---|--|--|
|---|--|--|

Table 3. Analysis populations

7.3 Covariates and Subgroups

(ICH E3; 9.7.1, 11.4.2.1. ICH E9; 5.7)

There are no obvious covariates in the study intervention. However, the risk of anesthesia is the primary concern in our study group demographic. We will record the health history and comorbidity of patients to indicate the underline risk of anesthesia. In addition, the patient with a higher BMI (>30) in the sedative/anesthesia group (at least 30 patients) will be further stratified into a subgroup to represent the patient with higher risk. Besides, at least 40 patients will be assigned to a non-anesthesia stage assessment in order to represent the ordinary patients in the health care facilities.

The recording in the sedative/anesthesia group will divide into three periods, 1. Induction, 2. intraoperative, 3. PACU. All data will be analyzed in the same procedure to indicate non-inferiority of Airmod with EtCO2.

7.3.1 Multi-center Studies

(ICH E3;9.7.1, 11.4.2.4. ICH E9; 3.2)

This study is intended to conduct in 2 sites in Taiwan, with an equal number of patients who will be expected to enroll in all sites but competitive.

7.4 Missing Data

(ICH E3; 9.7.1, 11.4.2.2. ICH E9;5.3. EMA Guideline on Missing Data in Confirmatory Clinical Trials)

The missing data in this study is referring to the non-detecting period of each device, which is excluded from the final comparison. The mean non-detecting period will be reported as a baseline variable in the units of minutes. The non-detecting period is the intrinsic NA value from the device record. It could represent the estimation is out of detecting range, or the device is calibrating itself (which is a basic function of the Capnostream[™]35). All of the recorded data will be controlled and monitored by Data and Safety Monitoring Board (DSMB) to ensure data integrity.

In our study, the NA value of intrinsic estimation will show an "NA" or "--" to the user interface of the device, just as the other vital sign monitor. The user interface delivers a clear message for the

malfunction period. It will not affect or increase the risk of respiratory rate measurement.

7.5 Interim Analysis and Data Monitoring

Per FDA required, (ICH E3; 9.7.1, 11.4.2.3. ICH E9; 4.1, FDA Feb 2010 "Guidance for Industry Adaptive Design Clinical Trials for Drugs and Biologics"). A Data and Safety Management Board (DSMB) will organize the regular meeting by the charter of DSMB. The interim analysis and data/safety monitoring should be evaluated in the meeting with regular meeting minutes. Data will be monitored under standard operation procedure of contract research organization and site management organization to prohibit protocol deviation.

7.5.1 Purpose of Interim Analysis

Due to uncertainty about the efficacy aspect, the interim will allow learning to influence the subsequent design of the study at DSMB. The whole ITT data will be analyzed in the interim analysis to evaluate the objective of this study. By evaluating the efficacy in the primary endpoint at this stage can determine the early success of its non-inferiority.

7.5.2 Planned Schedule of Interim Analysis

The interim analysis will be performed at the enrollment of 150 subjects (must include at least 30 nonanesthesia state patients enrolled) during the study period.

7.5.3 Stopping Rule

We're proposing not to apply the stopping rule for efficacy analysis in this study. Therefore, a failure end point in the interim analysis will not prohibit the following study. However, by the charter of DSMB. They are obligated to monitor, and terminate the study on a serious protocol deviation, or server medical device related adverse events reported.

7.5.4 Analysis Method to Minimize Bias

The whole ITT data set will be included in the interim analysis. A minimal sample size of 30 patients in each subgroup are required as a constrain to minimize the bias.

7.5.5 Adjustment of p-value

On the confidence interval analysis in this study, we adopt OBrien-Fleming to determine the nominal significance level α =0.00153 at the interim analysis for the 150 samples. Furthermore, at the end of the study the O'Brien-Fleming determines the nominal significance level at 0.02450 to establish the target of our study confidence interval.

7.5.6 Practical Measures to Minimize Bias

- CDA will perform the interim analysis.
- Members of DSMB will see any data or analyses in the interim and make decisions.
- All information will be publically available following an interim analysis.
- All information will be provided to the sponsor and investigators.
- CDA will perform the final analysis.

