6.3 MEASURES TO MINIMIZE BIAS: RANDOMIZATION AND BLINDING

This study will not be randomized and blinded.

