Activity level	Prior to discharge home, the patient's activity level must be at baseline. Patient must be able to ambulate at preoperative level.
Nausea and vomiting	Prior to discharge, the patient must have minimal to no nausea and vomiting.
Pain	Pain/discomfort must be at a level identified by the patient as tolerable. The location, type and intensity of pain should be consistent with anticipated postoperative discomfort.
Surgical bleeding	The surgical site must be free from excessive or unexpected bleeding/ drainage.

The breathing sounds and the partial pressure of CO₂ will then convert to the breathing counts and CO₂ waveform respectively using self-developed software written from Python and Matlab, the data will be recorded in Microsoft Excel and RR will eventually be calculated manually by trained personnel for each result.

During the study, if the study staff indicates the breathing sounds or the partial pressure of CO₂ is affected, for instance, an obviously external sound, moving the patient, nasal cannula drop, blocked, or other situation identify by the investigator. Such start/stop time of event(s) will be recorded in CRF, accurate to second. Such affected data or missing data will be excluded in the final comparison as such event(s) may be affecting the study result, determined by the investigator during the monitoring period.

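### SAP 7.5.6 releases all interim results to investigators, sponsor and public while up to 150 further subjects are still to be recorded, censored and scored without blinding

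*SAP*

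**What the plan says.** **Release.** SAP 7.5.6, headed as practical measures to minimise bias, contains two statements: "All information will be publically available following an interim analysis" and "All information will be provided to the sponsor and investigators". It also says "Members of DSMB will see any data or analyses in the interim and make decisions". Neither document restricts or delays the release.

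**Design influence.** SAP 7.5.1 says "the interim will allow learning to influence the subsequent design of the study at DSMB". It does not list which features may change. It adds: "By evaluating the efficacy in the primary endpoint at this stage can determine the early success of its non-inferiority".

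**No stop.** SAP 7.5.3 proposes "not to apply the stopping rule for efficacy analysis in this study", and SAP 7.1 places the final analysis at 300 subjects.

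**No blinding.** Protocol 6.3: "This study will not be randomized and blinded".

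**Who shapes the primary data.** Protocol 8.1 has staff record the start and stop of disturbing events, including any other situation that the investigator identifies, and says "Such affected data or missing data will be excluded in the final comparison". Protocol 9.4.2 applies investigator-reported failure periods, confirmed by the principal investigator, to the paired non-inferiority test. Under SAP 8.2.1, ManCRR is scored by researchers and verified by the principal investigator.

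**The concern.** The comparator in the primary endpoint is a human reading, and the data that enter the test depend on human decisions to exclude. People who make those decisions are among those who would receive the cumulative result halfway through. Once they know how Airmod stands against the margin, the same noisy minute or ambiguous waveform may be judged differently, without any intent to mislead.

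The group-sequential adjustment gives no protection against this. It assumes that the rules for generating, excluding and scoring data in the second half do not depend on the first-half result. An open list of possible design changes weakens the same assumption. At stake are the overall one-sided type I error of 0.025, the credibility of the second-half estimate, and the stricter 2 bpm comparison.

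**Working it through.** **1. Are the stated levels right?** Inputs from SAP 9.1 and the interim table in 9.1.1: one-sided alpha 0.025; looks at 50% and 100% information; nominal levels 0.00153 (z = 2.9626) and 0.02450 (z = 1.9686).

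- O'Brien-Fleming-type spending at t = 0.5: 2 × [1 − Φ(z(0.9875)/√0.5)] = 2 × [1 − Φ(2.2414/0.7071)] = 0.001525, so z = 2.9626.
- Final bound: solve 1 − P(Z1 < 2.9626, Z2 < c) = 0.025 with correlation √0.5. This gives c = 1.9686, nominal p = 0.02450.
- Overall one-sided error with the stated bounds: 0.0250.

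The plan's figures are reproduced. The 0.02450 is the nominal level at the last look; the rate to protect is the overall 0.025. The calculation covers two looks at data collected under fixed rules, and nothing else.

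**2. How many subjects follow the release?** The interim is triggered at 150 enrolled, so at most 300 − 150 = 150. Recruitment is not said to pause, and scoring takes time, so the number could be smaller.

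**3. What could a shift do?** The documents give no basis for the size of a shift. The following is an illustration under two assumptions: the pilot σ of 3.29647 (SAP 9.1) is the SD of subject means, and all 150 later subjects shift equally. The shift is set at 0.5 bpm, with half and double that value as a range.

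- SE at n = 300: 3.29647/√300 = 0.190 bpm.
- Movement of the final mean: shift × 150/300.

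| Assumed second-half shift (bpm) | Final mean moves (bpm) | In SE (÷ 0.190) | Share of 3 bpm margin |
|---|---|---|---|
| 0.25 | 0.125 | 0.7 | 4% |
| 0.5 | 0.25 | 1.3 | 8% |
| 1.0 | 0.5 | 2.6 | 17% |

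- Distance from zero difference to the margin: 3/0.190 = 15.8 SE.
- The final test passes when the mean exceeds −3 + 1.9686 × 0.190 = −2.625 bpm. In the middle row, the verdict flips only if the unbiased estimate lies between −2.625 − 0.25 = −2.875 and −2.625.

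**4. Upper illustration of type I error.** This is a simulation with 40,000 replicates, true difference exactly −3, subject-level SD 3.29647, and the least favourable second-half subjects removed. Removing 0, 2, 3, 8 or 15 of 150 gives overall error of about 0.025, 0.05, 0.07, 0.17 and 0.38. This is fully selective removal of whole subjects, whereas the plan censors periods within subjects. It is a worst case and not a prediction.

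**The case against.** **What stands against the point**

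- The study is open-label from the first subject and staff can see both monitors, so the release adds only the cumulative result to an existing weakness.
- Discretion has limits. Event times go into the CRF to the second during monitoring (Protocol 8.1), before manual rates are calculated. Events carry codes (SAP 11), missing episodes are reported to the DSMB (SAP 8.3), some exclusions are values the device itself returns as not available (SAP 7.4), and an interim snapshot is kept (SAP 7.5.7).
- The release has no date. Immediate release is the natural reading, but not the only one.

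These limits document the decisions without masking them, and the trigger for other situations stays open. They reduce the likely size of the bias; they do not remove it.

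**Stronger readings that the documents do not support**

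- A reader might infer that investigators may redesign the trial. SAP 7.5.1 places design influence with the DSMB, and no section lets investigators alter endpoints, margins or exclusion rules.
- A reader might infer that the judgements on less sensitive periods and the first effective breath inflate the primary type I error. They feed secondary endpoints 1 and 3 only (SAP 9.2.1; Protocol 9.4.3), which are exposed separately. The less sensitive periods are moreover to be determined in advance.
- A reader might infer that the primary conclusion is unsafe. With the margin about 15.8 SE from zero difference under the assumption above, a modest shift matters only close to −3 bpm.

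**Conclusion.** The point holds, and the text should be changed. SAP 7.5.6 prescribes a release that works against its own heading, and 7.5.1 leaves open which design features may follow the interim. The alpha split is correct but answers a different question: it does not cover exclusions, scoring or design changes made with knowledge of the interim result.

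That the documents say this is certain; how much it would matter is not. Up to 150 of 300 subjects could be affected. The bias cannot be sized from the documents: the shifts in the table are assumed, and σ may not be the SD of subject means, since SAP 9.1 works with per-minute counts. A change in the primary verdict requires a true difference near −3 bpm. Away from that, the second-half estimate and the 2 bpm comparison in SAP 9.2.4 could still be biased.

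**What to change.** 1. Delete the two release statements in SAP 7.5.6. Keep interim results with the clinical data analyst and the DSMB until the last recording is made and the exclusion lists and manual scores are locked. Allow earlier disclosure to the sponsor only if the 0.00153 boundary is crossed or the DSMB acts on safety.
2. State in SAP 7.5.1 that endpoints, margins, exclusion rules and sample size will not change on interim efficacy data.
3. Reconcile 7.5.1 (early success, design change) with 7.5.3 (no efficacy stopping rule).

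**Cost:** wording in the SAP and the DSMB charter, and the sponsor gives up early sight of a result that did not cross the boundary. Publication after lock still gives the intended openness. The change removes only the bias added by the interim release. The open-label exclusion and scoring of all 300 subjects would need separate measures, such as readers masked to AirRR and a sensitivity analysis without investigator exclusions.

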7.5.7 Documentation of Interim Analysis

Snapshots of the data available at the interim analysis should be preserved, as should all documentation of analysis plans, programming code and reporting provided at the interim. It should be possible to recreate the decision process from the trial archive by CDA.

8 Summary of Study Data

All of the continuous variables in the subject demography will be summarized using the following descriptive statistics: n (sample size), mean, standard deviation. The proportion and percentages (based on the non-missing sample size) of observed levels will be reported for all categorical measures (for instance, gender, principal operations). In general, all data will be listed, sorted by site, and trial period. All summary tables will be structured with a column for each device under test in the order (Airmod, Capnostream[™]35) and will be annotated with the total population size relevant to that group, including any missing observations.

Only deviations from the general overview will be noted in the subsequent sub-sections within section 9.

8.1 Subject Disposition

All of the subjects are enrolled and completed the study on the same day. There is minimal risk for following up with the candidates.

Fig 2. Subjects disposition

The whole screening and recruitment process will take place in the pre-anesthesia evaluation clinics to reveal the detail of this clinical study and we are proposing to enroll 300 patients with their informconsent form. A subset of patients (20 patients) will be randomly subjected to the non-anesthetic group and record their respiratory rate by both devices in the preparation room. The other candidates will proceed to their original operation/examination and we will record them with both devices through the whole procedural sedation process (from IV induction to discharge of PACU). Within this procedural sedated and anesthetic group a subset of patients (20 patients) will be asked to stay in the PACU for another 15~30 minutes after they are eligible to discharge, which means they are conscious clear and the recording of this period will be allocated to the non-anesthetic group in the future analysis.

The summary statistics will be produced in accordance with section 9.

Evaluating the Non-Inferiority of Airmod to Capnostream™35 on Respiratory Rate Monitoring and User Experience Clinical Evaluation

8.2 Derived variables

8.2.1 Manual-scored Capnography respiratory rate (ManCRR) originated from Capnostream[™]35 (K150272, Medtronic)

Manual scored capnography respiratory rate is a derived variable from the capnographic recording of Capnostream[™]35 device, the recording trace will be acquired from the original device record, analyzed by researchers with self developed software, and verified by the principal investigator. The verified data will be further integrated into the case report form as the ManCRR and compared with AirRR.

8.2.2 Manual-scored respiratory rate of auscultation sound (ManARR) originated from AS-101

Manual scored respiratory rate of auscultation sound is a derived variable from the auscultation recording of AS-101 and the original wav file was created by the Airmod. The acoustic waveform will be further processed and displayed on labeling software (Open Source by Heroic Faith medical Science: arXiv:2101.01352). The annotation will be conducted by the researcher in our study and respiratory rate would be estimated upon the analysis of the inhalation and exhalation annotation.

8.2.3 F1-socre

The F1 score is a weighted average of precision and recall for binary classification prediction models. In the secondary end goal "The accuracy of inhalation classification in the segmentation basis" is presented by F1-Score of the ground truth (manual score auscultation sound inhalation event) and the prediction (Airmod inferencing result on inhalation event). We will compare the result on a time series segmentation basis. The confusion matrix is determined by the classification result on manual score auscultation (consider as Actual measurement) and Airmod inferencing result (consider as Prediction measurement).

Airmod inferencing

| | | Inhale | Not Inhale |
|----------------------|------------|---------------------|---------------------|
| Scored on sound | Inhale | TRUE Positive (TP) | FALSE Negative (FN) |
| Manual Auscultati | Not Inhale | FALSE Positive (FP) | TRUE Negative (TN) |

Fig 3. Classification and abbreviation of outcomes of manual scored auscultation sound and Airmod inferencing.

The F1-score is defined as :

Precision = TP / (TP+FP) Recall = TP/ (TP+FN) F1-score = 2/ (Precision⁻¹ + Recall⁻¹)

8.2.4 MAPE

The MAPE (mean absolute percentage error) is a derivative of the accuracy as percentage measurement. The performance is metriced by MAPE of the A_t as the observed value (ManARR) and the F_t as prediction value (AirRR). We will compare the results based on total recording time (by minute).

The MAPE is defined as:

 $A_t = ManARR$ $F_t = AirRR$ n = Total recording time (by minute) $MAPE = 1/n (\Sigma((A_t-F_t)/A_t))$

8.2.5 Bland-Altman analysis

The Bland-Altman analysis is widely used to measure the consistency of continuous data from two distinct measurements. It combines the quantitative analysis of LoA (limits of agreement) and the qualitative analysis of scatter plot to show an instinctive evaluation between two methods of their correlation. Each of the n samples is then represented on the graph by assigning the mean of the two measurements as the x-value, and the difference between the two values as the y-value. The repeatability of RR measurements from Airmod (AirRR) and CapnostreamTM35(K150272, Medtronic) (CapRR) will be compared with ManCRR separately under the sampling rate: 1 sample point per 60 seconds, the differences are representing into Δ G_A and Δ G_E, while the S(x,y)=((Δ G_A+ Δ G_E)/2, Δ G_A- Δ G_E). To compare an estimate of this to the LoA, the two LoA are the mean value of x separately ±1.96SD. (doi: 10.1080/10543400701329422)

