Bland-Altman analysis is used to measure the consistency of continuous data from two distinct measurements. Therefore, the likelihood of AirRR and ManCRR will be quantified and visualized on the assumption of fixed observer and pairs Bland-Altman analysis. It combines the quantitative analysis of LoA (limits of agreement) and the qualitative analysis of scatter plot to show an instinctive evaluation between two methods of their correlation. Each of the n samples is then represented on the graph by assigning the mean of the two measurements as the x-value, and the difference between the two values as the y-value. By this graphical method, we can extend a simple logarithmic transformation approach to data where there is a relationship between difference and magnitude. We discuss the importance of repeatability of RR measurements from each equipment and compare an estimate of this to the LoA. [20] In this case, if the difference of RR measured from two equipment are in the 95% LoA, we will say that RR measured from these two equipment are correlated and acceptable.

$$S(x, y) = \left(\frac{\Delta G_A + \Delta G_E}{2}, \Delta G_A - \Delta G_E \right)$$

3. Use paired t-test to compare the response time of Airmod versus Capnography on Capnostream™35 after administration of jaw thrust. In the target of $p<0.05$ indicates significance. The principal investigator and research members will determine the apnea period and the first effective breath.

The paired t test can be used when the two groups under comparison are dependent on each other. [21] By acquiring the T value from paired t-test, we can obtain the p value indicating the significant difference level via t-distribution table or Microsoft Excel. A p value less than 0.05 would indicate that Airmod is able to resume RR estimation after proper intervention faster than Capnostream™35.

$$t = \frac{\bar{X}_1 - \bar{X}_2}{\sqrt{\frac{(s_1^2 + s_2^2)2\rho s_1 s_2}{n}}}$$

4. Capnography is inherently limited in certain circumstances which may cause ineffectively detecting CO₂, including movement, nasal cannula drop, blocked, or other situations. Airmod is superior to capnography in these limitations since it detects and measure breath sound directly.

4.1 The difference of ManCRR minus AirRR and ManCRR minus CapRR indicates non-inferiority at margin of 3 bpm (M1) and sampling rate 1Hz.

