4.4 Endpoints

Primary Endpoint:

The difference between AirRR and ManCRR, which is greater than -3 establishes non-inferiority. The unit in this calculation is bpm and sampling rate is 1 Hz.

Secondary Endpoints:

1. The accuracy of inhalation classification in the segmentation basis is greater than 82.5% at the 95% Cl. The performance metrics (F1-socre, MAPE) at event level will be demonstrated and target for F1-score > 0.8, MAPE < 0.5.

2. To measure the agreement of AirRR and ManCRR on concordance correlation coefficient, and on their mean and bias by Bland-Altman analysis.

3. Use paired t-test to compare the response time of Airmod versus Capnography on Capnostream[™]35 after administration of jaw thrust. In the target of p<0.05 indicates significance.

4.1. The difference of ManCRR minus AirRR and ManCRR minus CapRR indicates non-inferiority at margin of 3 bpm (M1) and sampling rate 1Hz.

4.2. The difference of ManCRR minus AirRR and ManCRR minus CapRR indicates non-inferiority at margin of 2 bpm (M2) and sampling rate 1Hz.

5. The absence of unanticipated serious adverse device effect (USADE) during study period and the questionnaire.

Evaluating the Non-Inferiority of Airmod to Capnostream™35 on Respiratory Rate Monitoring and User Experience Clinical Evaluation

[Time Frame:

Non-Anesthesia Stage: Up to 40 patients will be randomly assigned to non-anesthesia stage assessment, the measurement will be evaluated after enrollment with ICF, at the non-operating room (NOR) area. (5~30 minutes)

Procedure Stage: From firstly anesthetic administration to end of procedure. (Depends on procedure 10mins ~ few hours)

Transportation Stage: During transportation of subjects. (1~10 minutes)

Post anesthesia care unit stage : From subjects arrive post anesthesia care unit (PACU) to discharge from PACU (PAR or PADSS score \geq 9) (At least 15 minutes)]

5 Study Methods

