8.6 Treatment Compliance

Not applicable.

9 Efficacy Analyses

To demonstrate the non-inferiority, the Efficacy Analyses included all of the intent to treat population; it followed the objective of study endpoint to measure respiratory rate performance of Airmod (AirRR) in comparison with the reference device (ManCRR and CapRR). The respiratory rate estimation of each device under test (DUT) is described in the unit of the respiratory count per minute from each measurement over time (sampling rate at 1Hz) regardless of actual cause of inhalation event detected by DUT. The efficacy of agreement in the secondary endpoint is evaluated by Bland Altman analysis, a bias between mean and difference, and 99.69% CI at interim analysis and 95.1% at final analysis of the difference between DUTs in an unit difference plot (unit = breaths per minute). Subgroup analysis of each endpoint focuses on various sections and scenarios of anesthesia (from preparation, induction,

interoperation, transportation, and post anesthesia care unit). An obesity group (BMI >=30) is particularly selected to indicate the high risk patients in the procedural sedation and they will be tested as a stratified subgroup in all of the study endpoints.

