the actual measurement of the respiratory event.

9.2.2 Analysis to measure the agreement between AirRR and ManCRR.

Bland Altman analysis, and concordance correlation is adopted to measure the agreement between AirRR and ManCRR. The quantitative results of respiratory rate from these devices under test over time are evaluated by the above mentioned method to analyze the mean and bias from the plot and concordance correlation coefficient.

Fig 9. Bland Altman between AirRR and ManCRR (Example)

Fig 10. Correlation between AirRR and ManCRR (Example)

Fig 11. Correlation between AirRR and ManCRR during induction period (Example)

Evaluating the Non-Inferiority of Airmod to Capnostream™35 on Respiratory Rate Monitoring and User Experience Clinical Evaluation

Fig 12. Correlation between AirRR and ManCRR during Inter-operation period (Example)

Fig 13. Correlation between AirRR and ManCRR during transportation and PACU period (Example)

Also, we apply a sensitivity test for Airmod by comparing the reference method at each time point and calculating the absolute deviations in breaths per minute (bpm). As a measure of accuracy, absolute deviations were calculated as a percent of reference.

Percent absolute deviation were averaged for each subject yielding overall measures of accuracy. To evaluate the accuracy of Airmod, the individual percent absolute deviation was compared for each monitoring time point by subtracting ManCRR from AirRR and then averaged within subject. A paired t test was used to evaluate significance across subjects.

To measure the precision of Airmod for each subject, the standard deviation of percent deviations (in nonabsolute value) was calculated. The precision of Airmod was compared through a paired t test of the subject-specific standard deviations of Airmod's percent deviations from reference.

9.2.3 Analysis to evaluate the response time of the first breath detection followed by administration of jaw thrust during the apnea period. The 3rd secondary objective is to compare the response time of Airmod versus Capnography.

Use paired t-test to compare the response time of Airmod versus Capnography on Capnostream[™]35 after administration of jaw thrust. The target of p<0.05 indicates significance difference.

Evaluating the Non-Inferiority of Airmod to Capnostream™35 on Respiratory Rate Monitoring and User Experience Clinical Evaluation

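### SAP 8.2.5 builds the Bland-Altman plot from the wrong pair of quantities and centres the limits of agreement on x, so as printed it does not deliver the AirRR-against-ManCRR analysis of secondary endpoint 2

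*SAP*

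**What the plan says.** **The pair.** SAP 4.4 states secondary endpoint 2 as: "To measure the agreement of AirRR and ManCRR on concordance correlation coefficient, and on their mean and bias by Bland-Altman analysis". SAP 9.2.2 repeats the pair: "Bland Altman analysis, and concordance correlation is adopted to measure the agreement between AirRR and ManCRR". Its Fig 9 caption names the same two series and no third. Protocol 9.4.3 item 2 agrees: "the likelihood of AirRR and ManCRR will be quantified and visualized on the assumption of fixed observer and pairs Bland-Altman analysis".

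**The formula.** SAP 8.2.5 starts with the usual axes: "assigning the mean of the two measurements as the x-value, and the difference between the two values as the y-value". It then brings in CapRR. AirRR and CapRR "will be compared with ManCRR separately under the sampling rate: 1 sample point per 60 seconds", the two resulting differences are named ΔG_A and ΔG_E, and the plotted point is S(x,y) = ((ΔG_A+ΔG_E)/2, ΔG_A−ΔG_E). For the limits of agreement (LoA) it says "the two LoA are the mean value of x separately ±1.96SD". Protocol 9.4.3 item 2 prints the same S(x,y) without defining its terms.

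**Use of the limits.** Protocol 9.4.3 item 2 applies the 95% limits to the difference between the two devices. It declares the devices correlated and acceptable when the differences fall inside those limits.

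**The concern.** Two things do not fit together. First, the named comparison is Airmod against manually scored capnography, but the printed coordinates are built from two differences that each already have ManCRR in them. Subtracting one from the other does not give AirRR − ManCRR. Second, limits of agreement describe the spread of the plotted differences, so they belong around the mean of y. SAP 8.2.5 puts them around the mean of x, which the same section defines as a mean of two measurements, and does not say whose SD is meant. The SD matters further because the section takes one point per minute, hence many per subject, and cites a method for multiple observations per individual (same DOI as Protocol reference 20).

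A programmer who follows SAP 8.2.5 literally would report, under endpoint 2, a bias and limits for a quantity other than Airmod's error against the reference. The protocol's acceptance sentence would not reveal this.

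**Working it through.** **Inputs**
- Pair to be compared: AirRR and ManCRR (SAP 4.4, SAP 9.2.2, Protocol 9.4.3).
- Printed coordinates and limits: SAP 8.2.5.
- σ = 3.29647 (SAP 9.1, Table 6, pilot of 25 cases). The table does not say which quantity this is the SD of; I *assume* it is the SD of AirRR − ManCRR.
- Bias of 3 bpm: the primary margin, used only as a yardstick.
- *Assumed*, because the documents give no figure: SD of CapRR − ManCRR of 1, 2 or 3.29647; correlation of the two errors 0 or 0.5; normal errors.

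**1. The multiplier.** 2Φ(1.96) − 1 = 0.9500, so ±1.96 SD matches the 95% limits in the protocol. The multiplier is not at issue.

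**2. What the printed y is.** SAP 8.2.5 does not state the sign of the two differences.
- Same sign: y = (AirRR − ManCRR) − (CapRR − ManCRR) = AirRR − CapRR, and x = (AirRR + CapRR)/2 − ManCRR.
- Opposite sign: y = (AirRR − ManCRR) − (ManCRR − CapRR) = AirRR + CapRR − 2·ManCRR.

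Neither equals AirRR − ManCRR.

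**3. Mean of the printed y against the required bias** (bpm)

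| Airmod bias | Capnostream bias | Printed y, same sign | Printed y, opposite sign | Required: mean of AirRR − ManCRR |
|---|---|---|---|---|
| +3 | +3 | 0 | +6 | +3 |
| 0 | +3 | −3 | +3 | 0 |
| +3 | −3 | +6 | 0 | +3 |

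Required limits: 1.96 × 3.29647 = 6.46. At bias +3 they are −3.46 to 9.46; at bias 0 they are −6.46 to 6.46.

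**4. Share of plotted differences inside limits centred on x** (same sign). Let s_A and s_E be the SDs of the two errors and r their correlation. Then SD(y) = √(s_A² + s_E² − 2r·s_A·s_E) and SD(x) = ½√(s_A² + s_E² + 2r·s_A·s_E). The share is the probability that y lies within mean(x) ± 1.96·s, with s taken as SD(y) or SD(x).

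Worked case: Airmod 0, Capnostream +3, s_E = 1, r = 0. SD(y) = √(10.867 + 1) = 3.445, SD(x) = 1.722, mean(x) = 1.5, mean(y) = −3.
- With SD(y): limits 1.5 ± 6.75 = −5.25 to 8.25; share = Φ(3.27) − Φ(−0.65) = 0.743.
- With SD(x): limits 1.5 ± 3.38 = −1.88 to 4.88; share = Φ(2.29) − Φ(0.33) = 0.361.

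Over all assumed values (95% intended):

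| Airmod bias / Capnostream bias | SD of y | SD of x |
|---|---|---|
| 0 / 0 | 95% | 67–91% |
| 0 / +3 | 65–84% | 36–63% |
| +3 / +3 | 82–90% | 51–78% |
| +3 / −3 | 45–75% | 22–45% |

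**5. Direction of the change in width.** Over the same values the printed half-width is 5.64 to 9.14 with SD(y) and 3.38 to 5.60 with SD(x), against 6.46 for the required plot. Corrected limits could therefore be wider or narrower than the printed ones.

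**6. The acceptance sentence.** For roughly normal differences, the share within mean(y) ± 1.96 SD(y) is 0.950 whatever the mean and SD: the same at bias 0, SD 1 as at bias 10, SD 3.3. A condition that is met to the same degree at every level of agreement cannot detect poor agreement.

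**The case against.** The best defence is the word separately. It may mean two plots, AirRR against ManCRR and CapRR against ManCRR, with x standing loosely for each difference. On that reading the limits are correct. But S(x,y) in the same section combines both differences in a single point, and the section has already defined x as a mean. The defence works only if two of the section's own definitions are ignored.

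It is also fair to say that the intended pair is plain from the endpoint, SAP 9.2.2, the Fig 9 caption and the protocol, that SAP 8.2.5 opens with the standard axes, and that endpoint 2 carries no numerical target. An experienced analyst would probably produce the right plot. That limits the practical harm but leaves a stated formula that is wrong if followed.

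Some stronger readings are tempting but not supported:
- *Endpoint 2 and SAP 9.2.2 themselves require limits on the difference.* They name the pair and the mean and bias, and do not mention limits. The limits on the difference come from Protocol 9.4.3, with support from the axis definition in SAP 8.2.5.
- *SAP section 9 settles the matter.* Its phrase "95.1% at final analysis of the difference between DUTs in an unit difference plot" concerns a confidence interval, not limits of agreement, and a difference between devices under test could equally mean Airmod against Capnostream.
- *An error shared by both devices always disappears.* It cancels only when the two differences have the same sign; with opposite signs it doubles (+6 in step 3).
- *The non-inferiority result is at risk.* It is not. The primary test, the concordance coefficient (SAP 8.2.6), the percent deviations (SAP 9.2.2) and the outlier count (SAP 8.2.7) do not use this formula.

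**Conclusion.** The point stands as an internal contradiction that should be corrected before programming. As printed, SAP 8.2.5 does not plot AirRR − ManCRR under either sign convention, and it centres the limits on x with an unidentified SD. Nothing in the text available to me resolves the conflict.

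The algebra needs no assumption. The sizes do: they rest on reading the pilot σ as the SD of AirRR − ManCRR and on assumed CapRR biases, SDs and correlations, so they illustrate and do not predict. Within them, a 3 bpm Airmod bias can show as 0, and coverage can fall well short of 95%. With both devices unbiased and the SD of y used, coverage is the intended 95%, although the plotted quantity is still the wrong one.

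Separately, the protocol's acceptance sentence is uninformative about agreement. The reach of both defects is the Bland-Altman part of secondary endpoint 2 and no further.

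**What to change.** - In SAP 8.2.5 and Protocol 9.4.3 item 2, define y = AirRR − ManCRR, x = (AirRR + ManCRR)/2, and limits of agreement = mean(y) ± 1.96 SD. State that the SD comes from the already cited method for multiple observations per individual. Have SAP 9.2.2 refer to this definition.
- If CapRR is also to be shown, give it its own plot against ManCRR, defined in the same way.
- Delete the protocol sentence that calls the devices correlated and acceptable when differences lie in the 95% limits, and report the bias and the limits themselves.

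The cost is wording in two documents and a change of code; no new data are needed. The reported limits may come out wider or narrower than under the printed formula, so the change is best made before the analysis is run.
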